1.3 Schedule of Activities

This study consists of completion of a one-time online survey. The following type of information is contained within this one-time survey:

- Informed consent
- Demographics (includes gender, sexual identification, type of relationship. race, ethnicity, household income and age. No identifying information will be requested)
- Fertility history and diagnosis if any
- Mosie Kit use and experience
- Post-Mosie Kit use pregnancy success rate
- Perceived safety
- Perceived ease of use
- Effect of COVID-19 on family expansion plans
- Effect of COVID-19 on stress

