2.2 Background

Infertility is defined as not being able to get pregnant after one year of unprotected sex. About 6% of married and overall 12% of women ages 15 to 44 have infertility issues. Infertility issues can be of male or female origin. According to the CDC, in 35% of the infertility cases a male factor was found along with a female factor and in 8% of the cases the only identifiable cause was a male factor. Fertility is affected by multiple factors, one of which is the female's age. For this reason it is recommended that people anatomically female under the age of 35 seek help after one year of trying to conceive while those over the age of 35 should seek help after 6 months. One of the first options available is artificial insemination.

The first documented case of artificial insemination was done in the 1770s by John Hunger in London (Obmelet & Robays 2015). Subsequently J. Mario Sims reported his findings in the mid-1880s. Sims describes 55 inseminations. Unfortunately since he believed ovulation occurred during meneses, only one pregnancy was reported (Obmelet & Robays 2015). Research has come a long way since the early 18th century. Artificial insemination is now a much more frequent occurrence. Initially used by couples with male infertility (low sperm count and inherited Y-chromosome disease), later for couples with physiological and psychological dysfunction, such as retrograde ejaculation, vaginismus, hypospadias and impotence, and now

is very commonly used by people with no male partner (both single and those in lesbian relationships).

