3 OBJECTIVES AND ENDPOINTS

OBJECTIVES	ENDPOINTS	JUSTIFICATION FOR ENDPOINTS	PUTATIVE MECHANISMS OF ACTION
Primary			
The primary objective is to understand the outcome of using the at-home intracervical insemination Mosie kit, i.e. pregnancy rate after its use.	The primary endpoints is: Pregnancy Rate after up to 6 cycles. Another primary end point is to understand the rates of pregnancy in people who desire to get pregnant without intercourse (i.e. both single and those in LGBTQ relationships.	The ultimate objective of using the Mosie Kit is to end up pregnant. Thus pregnancy rate is a primary endpoint. Specifically, pregnancy rate in up to 6 (six) cycles will be examined as it is the typical standard timeframe for attempting to get pregnant using IVI or IUI before seeking an alternative method. People who have no known fertility issue who are trying to conceive without intercourse such as those who are in LGBTQ relationships or those who are not in any relationship at all will likely have higher pregnancy rates than those with known fertility issues of female origin. Women in LGBTQ relationships wishing to conceive might also have a higher pregnancy rate than those in heterosexual relationships where infertility might be caused by things like low sperm count, sperm motility issues or erectile dysfunction (ED).	The Mosie Kit is intended to be used to deposit semen at or near the cervix where the sperm will have an increased likelihood of entering the uterus and pairing up with the ovum resulting in a pregnancy. Pregnancy rates increase when sperm reaches the ovum and fertilizes it. In people with no known fertility issues, the Mosie kit deposits the semen where it is able to fertilize the ovum. People without infertility issues who want to get pregnant without sex by using the Mosie Baby are also more likely than people with known fertility issues to get pregnant.

Secondary			

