5 STUDY POPULATION

The study population will consist of all individuals who have purchased the Mosie Kit in the past 2-8 complete months prior to study initiation. All qualifying individuals will receive an invitation to participate. These individuals will typically be of child-bearing age, both females and males, and generally ages ranging 18-50 years old.

It is assumed that purchasing the Mosie Kit means the kit will be used as intended for at-home insemination. One of the inclusion criteria is to have previously used the kit. Therefore, the initial list of study participants will be drawn from people who have placed a purchase order within the prior 8 complete months; complete months are used with the expectation that the Mosie Kit would be used within the month post-purchase. If the study duration is expanded, additional potential participants will be invited who have purchased the kit at least 2 full months prior to being invited to participate in the study.

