9.1 Statistical Hypotheses and General Statistical Approach

The primary objective is to understand the outcome of using the Mosie kit for Intracervical insemination, i.e. pregnancy rate after its use. Specifically the hypothesis is as follows.

Primary hypothesis 1: Pregnancy rates using the at-home insemination Mosie Kit to deposit semen near or at the cervix (i.e. intracervical insemination) are equivalent or better than traditional in doctor's office intrauterine insemination (IUI). Conversely the null hypothesis is that the pregnancy rates using the at-home insemination Mosie Kit to deposit semen near or at the cervix do not have higher rates of pregnancy than in doctor's office IUI.

Analysis: Comparison of total rates of pregnancy using the Mosie Kit to the 10-20% rate reported for IUI by the American Pregnancy Association.

Primary Hypothesis 2: Pregnancy rates of LGBTQ couples or single women using the Mosie Kit where the female has no know fertility issues will be higher than that of heterosexual couples with a known fertility cause or those that are designated as having an unexplained fertility issue. The alternative hypothesis is that people with no known

fertility issues using the Mosie Kit will have less pregnancies than heterosexual couples with known fertility issues.

Analysis: Rate of pregnancy using the Mosie Kit will be obtained for the following groups: LGBTQ couples where carrying female has no known fertility issues, LGBTQ couples where carrying female has a known fertility issue, Heterosexual people with no known fertility issue, Heterosexual people with a known fertility issue, Single females with no known fertility issue and Single females with a known fertility issue. The rates of each group will be analyzed using descriptive statistics and the aggregate of the 3 groups with fertility issues will be compared with the aggregate of the 3 groups without fertility issues. An ANOVA will be used to compare the differences between groups.

Secondary Hypothesis 1: The participants perceived the Mosie Kit to be easy to use for its intended purpose. The alternative hypothesis is that the participants perceive the Mosie Kit to be difficult to use for its intended purpose.

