Appendix A: Online Survey Tool and Consent Form (Google Form)

This section shows what the Google Form will look like to the study participant. These are the questions the participant will be asked.

The first page of the study contains the consent form and the question that confirms the participant's agreement to participate.

There is skip logic for certain sections. For example, if the participant selects one cycle of using Mosie, the information related to cycles 2-6 will be skipped. If the participant selects that she is pregnant the questions related to the pregnancy will be asked, otherwise they will be skipped. If a donor was used, the questions related to producing a sperm sample will be skipped.

Note: Final language and questions might be tweaked or revised at any time to increase clarity.

MOSIE-001 © 2020 Mosie Baby Page 38

[figure not shown]
This is the inclusion/exclusion form.

If Participant selected to not participate in the study, he/she will see this screen next. If the participant said he/she is not 18 or older or has not used Mosie this screen will be displayed.

[figure not shown]

Qualifying participants will continue the survey on this page.

[figure not shown]

[figure not shown]
	ch of these diagnoses or issues do you believe are contributing to your rtility? *
	Not applicable
	PCOS
	Endometriosis
	Low AMH or low ovarian reserve
	Low Sperm count
	Sperm motility issues
	Erectile Dysfunction
	Performance issues or sexual anxiety, or inability to orgasm with partner
	Vaginismus or vulvodynia
	Tilted Uterus
	Multiple uterus/cervix
	Unexplained infertility
	Have only one functioning fallopian tube
П	Other:

[figure not shown]
No other method	is attempted			
Male/Female into	ercourse			
IVI or syringe oth	ner than Mosie			
IUI				
Femara				
Clomid				
IVF				
Cervical Cap				
Other:				
	None	1	2	3 or more
How many pregnancies have you had?	0	0	0	0
pregnancies	0	0	0	0
pregnancies have you had? How many live births have you had? How many pregnancies have you had that were	0	0	0	0
pregnancies have you had? How many live births have you had? How many pregnancies have you had	0	0	0	0

[figure not shown]

[figure not shown]
	0	1	2	3+
24-48 hours prior to ovulation	0	0	0	0
within 24 hours of ovulation	0	0	0	0
24-48 hours after ovulation	0	0	0	0
48+ hours after ovulation	0	0	0	0
Did you use Mosie fo Yes No	or another cy	cle?		

[figure not shown]

[figure not shown]

[figure not shown]

[figure not shown]

Mosie Kit Survey

* Required

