[figure not shown]
How did you or your partner time your ovulation? (Select all that apply.) *
Count days in cycle
Track vaginal or cervical fluids
Tracking changes in the cervix
Use ovulation predictor kit
Use an app to estimate ovulation
Basal Body Temperature
Wearable device
Did not time ovulation
Did using Mosie result in a pregnancy? *
O Yes
O No
Back Next Page 10 of 20

[figure not shown]
Never submit passwords through Google Forms.

 $This \ content \ is \ neither \ created \ nor \ endorsed \ by \ Google. \ \underline{Report \ Abuse} - \underline{Terms \ of \ Service} - \underline{Privacy \ Policy}$

Google Forms

Page 56

[figure not shown]

Safe process

Enjoyable

	Very Easy	Easy	Neutral	Difficult	Very Difficult
To collect the semen/sperm sample in the cup?	0	0	0	0	0
To draw up the semen/sperm in the syringe?	0	0	0	0	0
Insert the Mosie syringe into the vagina up to the handles?	0	0	0	0	0
To deposit the semen/sperm at or near the cervix using the syringe?	0	0	0	0	0
My overall impression on the ease of use	0	0	0	0	0
					Page 12 of 20
submit passwords to	through Google Fo				

MOSIE-001 © 2020 Mosie Baby Page 59

MOSIE-001 © 2020 Mosie Baby

Page 60

Pulled the syringe plunger back and forth to confirm it was functioning.

My partner washed their hands

Use a sperm friendly-lubricant.

Thawed out donor sperm from sperm bank

Prepared all items and have them handy ready to use.

Washed the penis

that	apply)?*
	Lie down in a comfortable position.
	Relax
	Receive oral sex
	Stimulate clitoris
	Use any vibratory or non-vibratory stimulation device intravaginally
	Have an orgasm
	Other:
	erall, how well were you able to use the Mosie syringe to inseminate yourself our partner? * Very Able
	our partner? *
or y O O O	our partner? * Very Able Able Not Very Able
or y 0 0 0 0	Very Able Able Not Very Able Not Able at All Volume at All Volume at All Volume at All Volume at All Able at All Volume at All Able at All Able at All
or y O O O	Very Able Able Not Very Able Not Able at All Volong did you remain laying down after using the Mosie syringe? * Less than 15 minutes

Willelf best descri	ibes your lying position? *	
On my stomach	n	
On my side		
On my back		
On my back wit	th my hips elevated by a pillow	
Other:		
O No		
O		
What type of sam	ple did you use? *	
What type of sam	ople did you use? * rom a sperm bank (frozen)	
What type of sam	rom a sperm bank (frozen)	

0 2000	thank 50%	
O 51%-	70%	
O 71% -	80%	
O 81%-	90%	
O 90%-	95%	
O 96%-	100%	

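### The fertility-issue item that very probably forms the Primary Hypothesis 2 groups is not tied to the time before kit use, so the outcome can influence the grouping and inflate the predicted difference

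*Combined protocol and SAP*

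**What the plan says.** - **Hypothesis and groups.** In section 9.1, Primary Hypothesis 2 predicts a higher pregnancy rate in LGBTQ or single users without a known fertility issue than in heterosexual users with a known or unexplained one. The analysis forms six groups, for example "LGBTQ couples where carrying female has no known fertility issues". It compares the three groups with an issue, pooled, against the three without, and names ANOVA. Section 9.4.1 sets 0.05 and prescribes a one-tailed test for directional hypotheses.
- **The item.** The readable fertility item in Appendix A asks which "of these diagnoses or issues do you believe are contributing to your" infertility. The first option is 'Not applicable'. Section 1.3 describes this block only as "Fertility history and diagnosis if any".
- **Timing.** Section 5 samples "all individuals who have purchased the Mosie Kit in the past 2-8 complete months prior to study initiation". The same one-time survey asks "Did using Mosie result in a pregnancy".
- **What is absent.** No section says when fertility status is fixed or which item assigns it. Section 4.3 rules out follow-up, and section 10.1.9.1 says no external records will be linked.

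**The concern.** The comparison is interpretable only if fertility status is a characteristic the user had before using the kit. The item asks what the respondent believes now, so the outcome can reach the classification by three routes.

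1. **Work-up after failure.** Section 2.2 says "those over the age of 35 should seek help after 6 months", and section 3 calls six cycles the "typical standard timeframe for attempting to get pregnant using IVI or IUI before seeking an alternative method". For some respondents both points fall inside the 2-8 month window. A user with no known issue who fails may be tested and then tick a diagnosis or 'Unexplained infertility'.
2. **Changed belief without work-up.** Section 2.2 states: "Infertility is defined as not being able to get pregnant after one year of unprotected sex". For a single or LGBTQ user not having intercourse, failed kit cycles may be the main reason to think an issue exists.
3. **The reverse route.** A user who is now pregnant and is asked what contributes to her infertility can reasonably tick 'Not applicable', even if she had an issue beforehand.

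All three push the observed difference in the direction Primary Hypothesis 2 predicts. Because the survey is anonymous, the error could not be found or repaired afterwards.

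**Working it through.** **Plan's own figures.** Section 9.2 gives ±4.4% for 500 surveys and ±5% for 384. With half-width = 1.96 × √(0.25/n), n = 500 gives 4.38% and n = 384 gives 5.00%. Both reproduce. They describe overall precision only; no power, effect size or group size is given for Primary Hypothesis 2.

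**Does this item form the groups?** Its twelve named options correspond to the twelve infertility sources listed under Tertiary Hypothesis 2 in section 9.1. They include unexplained infertility, which Primary Hypothesis 2 itself names. 'Not applicable' is the only readable no-issue answer. The inference is strong, but the plan does not state it.

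**Inputs.**
- From the plan: 500 surveys, level 0.05, one-tailed for directional hypotheses. Reference pregnancy rates are 10-20% (section 9.1) and up to 35% (section 4.1).
- Assumed: 250 users per group; the same true rate p = 20% or 30% in both; a fraction r of non-pregnant no-issue users recorded as having an issue, with r = 5%, 10% or 20%.

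**Expected rates, aggregate contrast.** Relabelled users join the issue group:
- no-issue rate = 250p / (250 − 250(1−p)r)
- issue rate = 250p / (250 + 250(1−p)r)

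For p = 20% and r = 10%, 250 × 0.8 × 0.1 = 20 users move. The rates become 50/230 = 21.7% and 50/270 = 18.5%. For p = 30% and r = 10%, 17.5 users move, giving 75/232.5 = 32.3% and 75/267.5 = 28.0%.

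| r | p = 20% | p = 30% |
|---|---|---|
| 5% | 20.8% vs 19.2% | 31.1% vs 29.0% |
| 10% | 21.7% vs 18.5% | 32.3% vs 28.0% |
| 20% | 23.8% vs 17.2% | 34.9% vs 26.3% |

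**Expected rates, hypothesis as worded.** A relabelled LGBTQ or single user cannot enter the heterosexual comparator and simply leaves the comparison. The no-issue rate rises as above, while the comparator stays at p.

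**False support with no true difference** (simulation, pooled two-proportion z-test; ranges span p = 20% to 30%):

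| r | Aggregates, one-sided | Hypothesis as worded, one-sided | Aggregates, two-sided (ANOVA-type) |
|---|---|---|---|
| 5% | 11-13% | 8% | 7-8% |
| 10% | 23-27% | 12-13% | 15-18% |
| 20% | 56-67% | 26-30% | 44-54% |

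With r = 0 the one-sided rate is about 5%.

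**Wider range.** For the aggregate contrast, with p from 10% to 35% and a no-issue share of 30-50%, the spurious difference is 0.7-2.3 points at r = 5%, 1.4-4.6 at 10% and 2.9-9.3 at 20%. One-sided false support is 8-13%, 13-28% and 25-69%.

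**Reverse route.** At p = 20% and r = 10%, suppose also that 10% of the 50 pregnant issue users tick 'Not applicable'. The rates become 55/235 = 23.4% and 45/265 = 17.0%, and one-sided false support rises from 23% to 56%.

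**The case against.** - **Missing survey pages.** The item's stem is cropped and several pages are figures not shown, so a lead-in or companion question that fixes timing could exist. This stands as a limit on certainty. No protocol text mentions such a question, and section 9.1 does not tie the groups to status before use.
- **No documented relabelling rate.** The fractions are assumptions, and the plan's own text limits them. Section 2.2 advises those under 35 to seek help after a year, recent purchasers cannot have completed six cycles, and section 1.1 expects participants to have prior fertility problems. Nothing supports 20% in particular, and at 5% the artefact is only about 1-2 points. This stands, although changed belief and the reverse route need no work-up.
- **Contrast and test.** The largest figures belong to the pooled contrast with a one-sided test. The hypothesis as worded and the named ANOVA give smaller ones. This stands, and all three are shown above.
- **Stronger readings.** A reader might infer that relabelling does create the hypothesised difference. The documents do not show that: they give no rate, and a true difference may exist. A reader might also infer that Tertiary Hypotheses 1 and 2 are biased in a known direction. They may be affected, but users diagnosed late could enter either the male-based or the female-based group, so no direction follows.

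**Conclusion.** The concern holds as a risk of outcome-dependent misclassification in a primary hypothesis. The readable item is unanchored and belief-based, is answered after the outcome is generally known, and very probably forms the groups. The bias can inflate or partly produce the predicted difference. Its size depends on an unknown relabelling fraction: at 5% false support is modestly above nominal, and at 20% it is several times nominal under every contrast and test examined. These figures assume equal true rates and 250 users per group. Confidence is moderate because some survey pages cannot be seen. The overall precision statement in section 9.2 is unaffected.

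**What to change.** Before launch:

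1. Reword the item to ask which diagnoses or issues were known before the first cycle with the kit.
2. Add a second item for issues diagnosed or first suspected after starting the kit.
3. State in section 9.1 that the Primary Hypothesis 2 groups and the infertility-source groups are formed from the pre-use item only, with the current-belief classification as a sensitivity analysis.
4. In the same place, say whether the primary contrast is the hypothesis as worded or the three-versus-three aggregate, since the size of the bias differs between them.

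The cost is one reworded item, one new item and a short addition to section 9.1; Appendix A already allows questions to be revised. The downsides are a slightly longer survey and some recall error about when a diagnosis was made. If an unshown page already fixes the timing, only the statements in section 9.1 and the sensitivity analysis are needed.

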6.1.2 Administration and/or Dosing

This study retrospectively examines the administration and dosing of semen during insemination in the home environment by using the Mosie Kit. The recommended dosing of semen to produce a positive pregnancy outcome is at least 2 times in a cycle. With the first dose preferably administered within 24 hours of the first signs of ovulation and the second one between 24-48 hours post ovulation confirmation. Since this study is retrospective, it will not influence dosing, but merely will collect information on the dosing frequency and timing.

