Analysis: Descriptive statistics surrounding the ease of use on a 5-point likert (very easy to very difficult) will be analyzed on five different aspects of use. Specifically, the steps of using the Mosie Kit (collecting a sperm sample, drawing up the sample in the Mosie syringe, inserting the syringe, and depositing the sperm at or near the cervix) and overall ease of use will be examined. Additionally questions related to use such as comfort, ease and safety of the process, enjoyable and intuitiveness of use (able to use it without instructions) will allow the user to rate their experience from Strongly agree to strongly disagree (5 point scale). The data will be plotted and examined as part of the analysis.

Secondary Hypothesis 2: The participants were able to use the Mosie Kit as instructed using the instructions contained in the kit. The alternative hypothesis is that the participants were not able to use the kit using the instructions contained in the kit.

Analysis: Descriptive analysis of perceived overall success rate will be analyzed. Additionally, descriptive analysis of the frequency of each expected behavior related to use of the kit will be examined.

Secondary Hypothesis 3: The participants reported they used the kit as intended, specifically, using it within 24 hours of initial signs of ovulation and again 24-48 hours after ovulation was confirmed or expected. The alternative hypothesis is that the participants report they did not use the kit as intended with respect to timing (within 24 hours of initial signs of ovulation and again 24-48 hours post ovulation).

Analysis: Frequency rates related to timing of insemination at all reported cycles will be analyzed. The data will be reported in both total number of attempts at each time point as well as percentage of attempts at each time point in comparison with total cycles where the Mosie Kit was used. T-tests will also be used in this analysis. Additionally,

amount of time lying after insemination and position of lying will be analysed using descriptive statistics and correlations with pregnancy rate.

Secondary Hypothesis 4: Participants reported they perceived the Mosie Kit to be a safe way to conceive. The alternative hypothesis is that participants did not perceive the Mosie Kit to be a safe way to conceive.

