Analysis: Descriptive statistics of pregnancy rates for groups with 1, 2, 3 and 4 or more inseminations per cycle will be used. These rates will then be compared to determine if there is a difference.

Tertiary Hypothesis 4: COVID-19 has affected people's family expansion plans. The alternate hypothesis is that COVID-19 has had no effect on people's family expansion plans.

Analysis: Descriptive analysis and a t-test will be conducted to examine this hypothesis.

Tertiary Hypothesis 5: There will be a decrease in pregnancy rates in those using the Mosie Kit during the Months of March - June.

Analysis: Descriptive statistics, graphing, ANOVA and multiple regression analysis will be used to examine this hypothesis.

Additional Analysis will also be conducted to explore why people might choose to use the Mosie Kit, how they actually use it, additional things they do when using the Mosie Kit to complement the experience, and whether they think their health care provider should recommend Mose as an conception option. Most of this analysis will be achieved using descriptive statistics, correlations, and t-tests.

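### The legible per-cycle timing grid has no row earlier than 48 hours before ovulation, so early inseminations cannot be recorded correctly

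*Combined protocol and SAP*

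**What the plan says.** Appendix A presents the survey as the set of questions participants will see. The one legible per-cycle timing grid has the answer columns 0, 1, 2 and 3+. Its rows are, in order, "24-48 hours prior to ovulation", "within 24 hours of ovulation", "24-48 hours after ovulation" and an open-ended row for 48 hours or more after ovulation. No row for anything earlier, and no row for other or unknown timing, is visible.

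Two planned analyses in section 9.1 need this kind of information:
- Secondary Hypothesis 3 (use as intended with respect to timing) reports the "total number of attempts at each time point", and the same as a percentage of all cycles in which the kit was used.
- Tertiary Hypothesis 3 compares pregnancy rates for "groups with 1, 2, 3 and 4 or more inseminations per cycle".

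Section 6.2 gives variation in timing and frequency as something the study wants to learn about, and section 6.4 intends to use the data to judge whether the minimum use was followed. Section 6.1.2 ties the first instructed insemination to the signs of ovulation ("With the first dose preferably administered within 24 hours of the first signs of ovulation"), whereas the grid is tied to ovulation itself.

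Appendix A also notes: "Final language and questions might be tweaked or revised at any time to increase clarity".

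**The concern.** The grid is open on the late side and closed on the early side. A respondent who inseminated three days before ovulation has no correct row. The only choices are to omit the attempt or to put it in a row that is wrong, and either way the attempt disappears from view as an early one.

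Early use is plausible here. The survey's own list of ways to time ovulation includes counting days, an app estimate and not timing it at all, and section 4.2 expects use to vary. The missing category is therefore part of the variation that section 6.2 sets out to describe.

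The error cannot be corrected afterwards. The survey is anonymous and completed once, with no follow-up (sections 4.3 and 10.1.3). Section 10.1.9.1 limits data checks to field types and completeness and excludes linkage to other records. None of these would detect an answer in the wrong row.

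A second consequence is conditional. If the number of inseminations per cycle is obtained by adding up this grid, an omitted early attempt also lowers the count, and a single answer of 3+ cannot be assigned to the group with 3 or the group with 4 or more.

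**Working it through.** **The plan's own figures.** The documents give no figure for the timing grid or for misrecorded inseminations. The only precision figures are in section 9.2, and both reproduce with half-width = 1.96 × √(0.25/n): 4.38% at n = 500 (stated as 4.4%) and 5.00% at n = 384 (stated as 5%). Neither depends on the grid.

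**Step 1: what the grid can hold.**

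| Time of insemination | Valid row? |
|---|---|
| More than 48 h before ovulation | none visible |
| 24-48 h before | yes |
| Within 24 h | yes |
| 24-48 h after | yes |
| 48 h or more after | yes, open-ended |

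**Step 2: what each response does to the data.**

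| Respondent's choice | Timing frequencies | Count, if summed from the grid |
|---|---|---|
| Omits the early attempt | one early attempt missing | one too low |
| Uses another row | attempt shown nearer to ovulation than it was, or on the wrong side | unchanged |

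The timing data are wrong in both cases. The count is wrong only in the first, and only if it comes from the grid.

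**Step 3: illustration for the count.** All inputs are assumptions. The documents do not say what share of inseminations is early. Section 2.2 gives 10-15% as a per-cycle range for intracervical insemination, but not by number of inseminations. Assume:
- each insemination is early with probability x, independently, with x = 5%, 10% or 20%;
- every early attempt is omitted and the count is summed from the grid;
- true per-cycle pregnancy rates are 10% (one insemination) and 15% (two), in groups of equal size.

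Share of two-insemination cycles that lose exactly one: m = 2x(1 − x).

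Recorded one-insemination rate: (10% + m × 15%)/(1 + m). The difference from 15% is therefore 5/(1 + m) points.

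| x | m | Recorded one-insemination rate | Difference |
|---|---|---|---|
| 5% | 9.5% | 10.4% | 4.6 points |
| 10% | 18% | 10.8% | 4.2 points |
| 20% | 32% | 11.2% | 3.8 points |

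Cycles in which both inseminations are early (x², that is 0.25% to 4%) would be recorded as zero, so they are not part of m.

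**Step 4: sensitivity.**
- The table keeps early one-insemination cycles in their group. If they are also recorded as zero and drop out, the difference is 5(1 − x)/(1 − x + m) = 5/(1 + 2x), which is 4.5 points at x = 5% and 3.6 points at x = 20%.
- If only half of the early attempts are omitted and the rest are put in another row, replace x by x/2. Then m is 4.9% to 18% and the difference is 4.8 to 4.2 points.
- If all early attempts are put in another row, the difference stays at 5 points and only the timing is wrong.

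**The case against.** **The pages are incomplete.** The question stem and several neighbouring screens are not shown, and other grids in the appendix came through broken. A separate question on the number of inseminations could sit on a missing screen, and neither section 9.1 nor section 9.4.3 says the count is summed from the grid. This stands, and it is why the count effect is stated only conditionally. A lost top row in the timing grid cannot be excluded either, but the first row follows directly after the column header, which makes that less likely.

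**A reader might infer that two-insemination cycles are recorded as one.** The documents do not support this as a fact. It needs an early insemination, a respondent who omits it rather than using another row, and a count taken only from this grid. None of the three is established.

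**A reader might also infer that use will look closer to the instructions than it was.** Omission does not do this. Section 9.1 takes all cycles of use as the denominator, so dropping an early attempt changes neither the on-window numerator nor the denominator. A cycle that then shows one attempt looks further from the two-insemination instruction. Misplacement into the nearest row would flatter adherence only if that row counts as compliant, which the documents do not say.

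**The effect is small and the data are soft.** With an assumed 250 cycles per group, the 95% half-width for 10% versus 15% is 1.96 × √(0.09/250 + 0.1275/250) = 5.8 points, well above the shrinkage of 0.4 to 1.2 points in the Step 3 table. Timing is recalled, and some respondents did not time ovulation, so a new row will not make every placement reliable. This stands. It limits the weight of the point, but does not justify leaving out the category.

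**Conclusion.** The point holds in a limited form. As legible, the grid cannot correctly record an insemination more than 48 hours before ovulation. Early use will be under-recorded in the frequencies for Secondary Hypothesis 3 and in the description of timing variation, with no matching loss on the late side. This conclusion rests only on the visible rows, and on the grid being repeated in the same form for the other cycles.

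The effect on Tertiary Hypothesis 3, including the limit set by the 3+ column, depends on the count being taken from this grid. Its size cannot be derived from the documents; the shrinkage from 5 points to about 4.6-3.8 points is an illustration on assumed inputs. Neither a general shift of two-insemination cycles into the one-insemination group nor an inflated adherence rate is shown. The analyses concerned are secondary and tertiary, and no primary endpoint depends on the grid. The change is worth making because it is cheap and the loss cannot be repaired later.

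**What to change.** Before launch, add a row for more than 48 hours before ovulation to the timing grid on each cycle page. This matches the open-ended late row and changes no instruction on use.

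Check the complete form for a separate item on the number of inseminations per cycle. If there is one, name it in section 9.1 as the source for Tertiary Hypothesis 3. If there is none, either ask the number directly for each cycle or collapse the top groups to 3 or more.

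The cost is one extra row per cycle page and, if needed, one short question. The revision note in Appendix A leaves room for both. If responses have already been collected on the grid as shown, report that early inseminations had no category and make no statement about how often they occurred.
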